7 TRIAL PROCEDURES

Process	Time
Community Mental Health Teams, and Therapy Hub Teams are notified of recruitment by poster, visits to team meetings, and email.	Prior to commencement of study
CMHT or Therapy Hub staff to discuss the trial with existing patients of the CMHT service. CMHT staff will gain consent for the trial team to contact the participant.	Prior to the commencement of study
Participant contacted by trial team. Brief information about trial provided. If participant is provisionally interested in joining the study, then they will be offered an initial appointment to be given the full participation information leaflet.	Prior to the commencement of study
Following the initial meeting, the participant will be given 7 days to decide if they want to be part of the trial.	0 days

After 7 days, the participant will be invited back to sign informed consent forms or withdraw from the study.	At 7 days
Participant contacted to advise them of the date of the introductory group.	At 1 months
Participants that complete the introductory group will become part of the baseline phase of the study.	At 4 months
Participants will have a baseline waiting period of 8 weeks. Outcome data will be collected during this phase. The participant will also start producing their MBT passport, and assessment collaboratively with a member of the treatment team.	At 8 months
Participants will begin MBT treatment for a period of 18 months. Outcome data taken weekly. Secondary outcomes and review of service use/self-harm taken every 6 months.	At 24-26 months
Follow up period will begin. Primary outcome data taken weekly.	Between 24-26 and 30-32 months
Qualitative interviews take place.	Between 30-34 months
Study end point. Data analysis and publication phase begins.	30-36 months
Dissemination of findings, publication.	Within 12 months following the last follow up data point of the final participant.

7.1 Recruitment

Participants will come from a Later Life MBT service in Manchester, which exclusively serves older adults and offers a comprehensive MBT program. The study aims to collect data from 10 older adults for an 18-month treatment duration. As the population is likely to have multiple physical comorbidities, the study will aim to recruit 14 participants, with the expectation that there will be some attrition in the screening and introductory phases.

Single Case Experimental Design studies consider several factors for power, including participant count, observations, inter-participant correlation, and the likelihood of false positives (Shadish et al., 2014). To ensure adequate power, we'll collect weekly outcome data on personality functioning using the LPFS 2.0 and data on loneliness using the Social Isolation Short Form 4a before, during and after the 18 months treatment from the participants.

Participants will be sourced from an existing later life MBT service. All will have a confirmed personality disorder diagnosis based on the DSM-5 structured clinical interview (SCID-5-PD) or subthreshold. Those not meeting this criteria will not be excluded from the service if MBT is clinically indicated. When participants fulfil only one criterium under the cutoff point at the SCID5-PD interview, they will also be included in the study, but it will be clearly indicated that they are 'sub-threshold' to a full diagnosis of personality disorder.

Typically, referrals to the later life MBT service come from older adult community-based mental health teams in England, overseen by the NHS. All study participants will receive standard treatment, including regular meetings with a mental health professional and periodic reviews with a consultant psychiatrist. No restrictions will be placed on participants seeking other treatments, though concurrent psychological treatments might be contraindicated.

All participants will be aged 65 or older, with no upper age limit. The study won't control for other demographics, except that participants must reside in Manchester. Free transport can be arranged for participants, and in rare cases, treatment can be provided at home or in hospital wards due to frequent treatment disruptions from physical ailments or illnesses in older adults.

7.1.1 Participant identification

To guarantee confidentiality, participants will receive both written and verbal information detailing the scope and limitations of confidentiality within the study. Information shared by participants will remain confidential and will not be disclosed to anyone outside the clinical or research team, barring urgent, life-saving circumstances. Outcome measure data will be securely stored, and participants will be allocated a unique identification number to safeguard their identities.

Identification of potential participants will be completed by members of the participants usual clinical team. No further recruitment will take place outside of later life community mental health teams.

Members of the research team will not have prior access to potential participants, who will be referred to the study by the community mental health teams. During the study, the therapists delivering the study intervention will record clinical information on the participants PARIS record, which is the local recording system used by the NHS trust. Outcome measurement data will be pseudonymized and will not be identifiable to members of the clinical team.

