Participant is not suitable for MBT

Referrer notified. Any risks clearly explained to participant and referring team.

Structured Clinical Interview for DSM-V Personality Disorder administered using both the screening tool and full interview.

Participant does not meets diagnostic criteria

Participant meets diagnostic criteria, or is 1 criterium below the diagnostic criteria.

Participant is invited to begin the treatment phase. Initial qualitative interviews completed.

Phase 3 - Treatment

Participant is invited to attend the MBT-Introductory group for 12 weeks.

Following MBT-I. Participants have an 8-week waiting period. This is the baseline phase. During this phase further assessment work is completed. Data collection via PROMIS questionnaires begins at the start of this phase on a weekly basis.

Participants are provided 18 months of MBT treatment. They are provided a weekly individual and group appointment. Data collection continues weekly.

After 18 months the participants end MBT. A review is completed with the participant, their consultant psychiatrist, and MBT practitioner.

Follow-up phase begins

Phase 4 – Follow-up

Participant begins follow-up phase

Each participant is asked to complete a short qualitative interview. This interview focuses on the acceptability of the intervention

Participants are contacted each week to complete the PROMIS questionnaires. 6 months of follow-up will be completed.

At the end of the follow-up period, participants are reminded of contact details for relevant individuals and informed of further details regarding future dissemination plans.

Study ends at the completion of all follow-up appointments.

Contributors support writing, dissemination and analysis of final anonymised data

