Dialog The Dialog Satisfaction Scale gauges 'patient satisfaction' concerning their quality of life and the treatment they receive. This 11-item scale can be analysed item-wise or by calculating a mean score across all items. In this study, an overall mean score will be used, which ranges from 1 to 7. Scores above 5 suggest high satisfaction, potentially indicating that secondary mental health care might no longer be necessary. Conversely, scores below 4 highlight explicit dissatisfaction, warranting "particular attention" (Mosler et al., 2020).

Columbia Scale: The Columbia Suicidality Response Severity Scale (CSRSS) offers a preliminary indication of an individual's suicide risk. It contains 6 items and total or mean scores range from 0 to 1. While it should be used alongside other risk assessment tools, it serves as an initial screening tool for potential suicide risk in adults. The scale has shown sensitivity to changes in suicidality over time (Posner et al., 2011).

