7.5 Long term follow-up assessments

In the 6 months after the treatment phase the participant will be asked to fill out the primary outcome questionnaires (LPFS 2.0. and Social Isolation Short Form 4.0.) on a weekly basis and the secondary outcome questionnaires (ReQoL,10, Dialogue and CSRSS) at the end of the follow up period for the purpose of the scientific research.

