10.8 Procedure(s) to account for missing or spurious data

The primary outcome data will be gathered weekly before each participant's individual MBT session, either by the therapist or via phone if the participant is absent. The secondary outcome measures will be collected by the research assistant. Patients will be attending at least weekly sessions at the location, so the research assistant and therapists will have regular contact with the participants to remind them to fill out the questionnaires.

In case of missing data we will try to find the reason that the participant did not fill out the questionnaire. In case of random missing data the data analysis contain an implicit imputation. In case of drop-out we will try to describe the reason for drop-out, because we are interested whether this treatment is feasible for older patients with personality disorders.

10.9 Other statistical considerations.

In case of slow recruitment rate an amendment to this protocol will be submitted to request for extension the recruitment period of 3 years.

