*ReQol: The Recovering Quality of Life (ReQol-10) scale tracks perceived changes in 'quality of life' over time. This 10-item scale is validated for individuals aged 16 and above. Scores range between 1 and 5, and a shift of 5 points on the scale indicates 'significant improvements' (Keetharuth et al., 2018).

Dialogue: The Dialogue Satisfaction Scale gauges 'patient satisfaction' concerning their quality of life and the treatment they receive. This 11-item scale can be analysed item-wise or by calculating a mean score across all items. In this study, an overall mean score will be used, which ranges from 1 to 7. Scores above 5 suggest high satisfaction, potentially indicating that secondary mental health care might no longer be necessary. Conversely, scores below 4 highlight explicit dissatisfaction, warranting "particular attention" (Mosler et al., 2020).

Columbia Scale: The Columbia Suicidality Response Severity Scale (CSRSS) offers a preliminary indication of an individual's suicide risk. It contains xx items and total or mean scores range from 0 to 1. While it should be used alongside other risk assessment tools, it serves as an initial screening tool for potential suicide risk in adults. The scale has shown sensitivity to changes in suicidality over time (Posner et al., 2011).

Initial screen and evaluation:

Structured Clinical Interview for DSM-5 Personality Disorders

This measure is a validated tool for assessing DSM-5 personality disorders. It has been used with both younger and older adults. There is a procedure for delivering the interview and scoring it. All three members of the team that will deliver this interview have been trained in its use.

Additional processes

To ensure adequate data collection, all outcome measurement forms will be provided to each participant weekly, at their face to face appointment. If the participant does not attend a session, then they will be asked to complete the questionnaire at the next available appointment. Data will be securely stored on a database that will not be accessible by the treatment team, and will only be accessible by the data management and collection team.

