11.2 Data handling and record keeping

Four systems will be used to manage data. The PARIS system for clinical data, a secure database for outcome measures, SPSS software to manage statistics, and the Single Case Designs app to managed data relating to SCD portion of the study.

For clinical data, including records of appointments, and clinical communication, this will be recorded on PARIS, which is the local NHS trust's recording software. Standard local processes will be followed, and adhered to.

Outcome data will be securely stored on a database, validated by the research and development team. The SOPs for the use of the system will be followed, and an audit trail of data changes will be maintained to ensure that there is no deletion of entered data. The system will be secure to protect against unauthorized access. Upon the commencement of the trial, a list of the individuals authorized to make data changes will be compiled. They will be responsible for data entry, maintain adequate backups of the data, and safeguarding the blinding of the trial to the clinical team. Source data will be archived. If data are transformed during processing, it should always be possible to compare the original data and observations with the processed data. Participant identification codes will be used to ensure identification of all the data reported for each participant.

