12 MONITORING, AUDIT & INSPECTION

Three areas of the study require monitoring. These include:

a) Consent, participant information onboarding process,

All initial appointments will be video recorded using MS Teams and stored. The video recordings will be reviewed for adherence to the protocol by the CI at the beginning of the study. All participants must be given all information in the participant information sheet verbally, as well as additional written copies to review following the first contact. Signed consent forms will be reviewed by the CI once at the beginning of the study for all participants. The CI will be based on site, where all of the initial contacts will occur.

b) Adherence to MBT treatment manual

All MBT individual and group sessions will be recorded. A sample of these recordings will be reviewed every 4 weeks by an accredited MBT supervisor. The research team will review tapes as peers throughout the programme, using the adherence checklist, as part of the weekly MBT clinical team meeting.

c) Data input, management, and storage.

The data collection team will be responsible for ensuring that the data collection, management, and storage accords with the study protocol. The CI for the study is part of the clinical team, and so will be unable to access the database containing outcome scores. As such the data collection team will peer review their adherence. The CI will supervise the members of the data collection team, ensuring that they are aware of the processes and procedures required. A named person external to the data collection team will monitor the database every 6 weeks for adherence to the protocol, and reporting any deviations to the CI.

d) GMMH R & I audit and monitoring

This study will be subject to audit and monitoring by GMMH's R and I team. This monitoring will occur in line with the relevant SOP (RDSOP11)

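### The concealment rules do not exempt the Columbia suicide-risk screen, and nothing makes a positive answer a risk event; the gap is clearest at the end of follow-up

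*Protocol*

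**What the plan says.** **Concealment.** Section 7.1.1: "Outcome measurement data will be pseudonymized and will not be identifiable to members of the clinical team". Section 11.1, after describing each instrument including the Columbia Scale: "Data will be securely stored on a database that will not be accessible by the treatment team". Section 11.2 makes the staff authorised to change data responsible for "safeguarding the blinding of the trial to the clinical team". Section 12(c): "The CI for the study is part of the clinical team, and so will be unable to access the database containing outcome scores".

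**The screen.** The Columbia Scale is a secondary outcome alongside ReQoL-10 and Dialog. Section 3.2 says of it: "While it should be used alongside other risk assessment tools, it serves as an initial screening tool for potential suicide risk in adults". Section 10.8 says who takes it: "The secondary outcome measures will be collected by the research assistant". In the six months after treatment, section 7.5 has participants complete "the secondary outcome questionnaires (ReQoL,10, Dialogue and CSRSS) at the end of the follow up period for the purpose of the scientific research". The trial flow chart (Phase 3) places this after therapy has stopped: "After 18 months the participants end MBT".

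**Response to risk.** Section 2.1 describes management within the therapy, a list of steps from the NICE self-harm guidance, contact with the care coordinator if the participant consents, and safeguarding advice where consent is withdrawn. It speaks of risk incidents and risk events without defining either. Section 9 covers adverse events, serious adverse events, suicide and life-threatening suicidal behaviour.

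**The concern.** Each of these arrangements is reasonable alone. Together they leave a research assistant who holds a positive suicide screen with an instruction to protect blinding and no instruction to pass the answer on. Section 9.6 gives the chief investigator clinical oversight of participant safety, yet section 12 keeps the outcome scores from that same person.

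Suicide is the only hazard named in the risk table in Appendix 1. Section 3.4 also expects that older people may hide self-harm and suicidal behaviour, and may not disclose it at baseline. On the protocol's own reasoning, the form may hold information that no clinician has heard in person. What is at stake is participant safety; no power or error-rate figure depends on it.

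**Working it through.** No figure in the protocol is in dispute, so the check is a comparison of texts plus one count.

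**Step 1. Does any concealment rule exempt the Columbia Scale?**
- Section 7.1.1 covers outcome measurement data in general and names no instrument.
- Section 12(c) covers outcome scores in general and names no instrument.
- Section 11.1 closes the database to the treatment team. Its paragraph is about forms handed out weekly, so it supports the general rule less firmly.
- Section 11.2 speaks only of blinding, again without an exception.

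Result: no exemption. The general rule rests mainly on sections 7.1.1 and 12.

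**Step 2. Does any text turn a positive answer into an action?**
- Section 2.1 mentions no questionnaire, no threshold and no duty on the research assistant.
- Sections 9.1, 9.2 and 9.5 concern events that have happened, not a screening answer.
- Appendix 1 lists community team care, psychiatrist review and crisis plans, with no link to Columbia answers.

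Result: no trigger is stated.

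**Step 3. Is the position the same at every time point?** No.
- *Forms up to the end of treatment.* Section 7.4 says all five questionnaires are already taken six-monthly in clinical treatment, and that the main change is weekly collection of the two primary ones. Section 5 keeps local policies in force unless the protocol expressly departs from them. Clinicians may therefore still see these answers. The text supports both readings.
- *End-of-follow-up form.* Section 7.5 takes it for research, and the flow chart has MBT already ended. The routine-use reading does not fit it.

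**Step 4. How many end-of-follow-up forms?** The places that list the secondary assessments all include one:
- Section 3.7 ends at 24 months, which section 3.3 makes up as 18 months of treatment plus 6 of follow-up.
- Sections 3.2 and 10.3.3 name the end of follow-up.
- Appendix 4 shows 1 in the follow-up column.

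With the planned 10 to 14 participants (trial summary; section 10.2): 1 × 10 = 10 to 1 × 14 = 14 forms, if every participant completes it. The form falls 24 − 18 = 6 months after MBT ends.

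**Step 5. What else would reach a clinician?**
- Community team contact at least monthly, and crisis care plans (Appendix 1).
- Adverse event assessments, one at baseline and one at follow-up (Appendix 4).
- The chief investigator's checks for adverse events at attendance (section 9.6).
- At 18 months, a review with the consultant psychiatrist and the MBT practitioner (flow chart).

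Each may bring the risk to light. None is started by the form.

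**The case against.** The strongest reply is that the protocol already manages suicide risk and does not block escalation. Much of that stands.

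- A reader might infer that the trial has no suicide-risk procedure. It has: section 2.1, section 9 and Appendix 1 describe one, and section 13.10 keeps every participant under the community team afterwards.
- A reader might infer that research staff are forbidden to tell clinicians. The confidentiality limit in section 7.1.1 concerns people outside the clinical and research teams, and lets even that limit yield when life is at risk. It permits sharing between the two teams; it does not require it.
- A reader might infer that every Columbia form is hidden from clinicians. Sections 5 and 7.4 make that uncertain for the earlier forms, so the general claim fails.
- A risk event is undefined but not restricted, and could be read to include a positive screen. Local policy or the participant information, neither of which is in hand, may say so. The protocol refers to no such procedure for this form.

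What survives is narrow. Permission and ordinary contact are not a trigger, and the only instruction to data staff that bears on sharing scores with clinicians is to protect the blinding.

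**Conclusion.** The point holds in limited form. The concealment rules do not exempt the Columbia Scale, and the protocol never makes a positive answer a risk event. The clear gap is one form per participant, 10 to 14 in all, at the end of follow-up. For earlier forms the text is ambiguous and no count of exposed forms is justified.

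This assumes the concealment rules are read as written, all participants complete the form, and no local procedure outside the file covers it. The number of positive answers cannot be estimated from the protocol. It is a cheap safety improvement and does not undermine the analysis.

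**What to change.** - **Sections 7.1.1, 11.1 and 11.2:** exempt the Columbia Scale, and only that scale. Keep concealment for the LPFS-BF 2.0, Social Isolation 4a, ReQoL-10 and Dialog.
- **Sections 2.1 and 7.5:** state that the research assistant checks each Columbia form when it is collected, including the one at the end of follow-up. State that a positive answer is a risk event, and that it goes promptly to the care coordinator or duty clinician under the consent and safeguarding steps already in section 2.1.
- **Threshold:** the trial team should name the items and answers that count, since the protocol does not print them.

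The chief investigator does not need database access for this, so section 12 can stand.

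The cost is a short amendment and a check by someone who already handles the form. The downside is that clinicians are partly unblinded on one secondary outcome, and escalation may slightly affect how self-harm and suicidal behaviour are entered in the clinical records from which those outcomes are taken. A simple log of escalations, reported with the results, would make that visible; it is optional.

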7.1.2 Screening

Before starting the program, participants undergo screening to assess their suitability for MBT. This stage addresses practical issues like attendance, transportation, and necessary adjustments for disabilities. Participants also receive an overview of MBT, its duration, and the existing evidence supporting its efficacy.

All participants will be assessed before commencing the study as to whether they meet the criteria for personality disorder. This will be confirmed on the DSM-5 structured clinical interview (SCID-5-PD). When participants fulfil only one criterium under the cutoff point, they will also be included in the study, but it will be clearly indicated that they are 'sub-threshold' to a full diagnosis of personality disorder.

Those not meeting these criteria will not be excluded from the service if MBT is clinically indicated, but they will not be included in the data collection, or wider research study. If MBT is not clinically indicated, then the clinical team will discuss appropriate care following the assessment process with the local CMHT.

